8.6.2. Extent of Exposure

A subject's extent of exposure to drug data will be generated from the drug administration data. Exposure data will be summarized by treatment group.

8.6.3. Adverse Events

Clinical and laboratory adverse events will be coded using the Medical Dictionary for Regulatory Activities (MedDRA). System Organ Class (SOC), High-Level Group Term (HLGT), High-Level Term (HLT), Preferred Term (PT), and Lower-Level Term (LLT) will be attached to the clinical database.

Events will be summarized on the basis of the date of onset for the event. A treatment-emergent adverse event will be defined as any adverse event that begins on or after the date of first dose of treatment up to the date of last dose of treatment. Continuing adverse events diagnosed prior to the start of treatment and worsening in severity grade, or non-serious adverse events at baseline which become serious, or adverse events resulting in treatment discontinuation after the start of treatment will also be considered treatment-emergent.

Summaries (number and percentage of subjects) of treatment-emergent adverse events (by SOC, and PT) will be provided by treatment group:

- Treatment-emergent adverse events
- Treatment-emergent study drug-related adverse events
- Grade 3 or 4 treatment-emergent adverse event
- Grade 3 or 4 treatment-emergent study drug-related adverse event
- Grade 2, 3, or 4 treatment-emergent adverse event
- Grade 2, 3, or 4 treatment-emergent study drug-related adverse event
- AE that caused permanent discontinuation from study drug
- AE that caused change in dose or temporary interruption of study drug
- Treatment-emergent serious adverse event
- Treatment-emergent study drug-related serious adverse event

8.6.4. Laboratory Evaluations

Selected laboratory data (using conventional units) will be summarized using only observed data. Data and change from baseline at all scheduled time points will be summarized.

Graded laboratory abnormalities will be defined using the grading scheme in [Appendix 5](#).

Incidence of treatment-emergent laboratory abnormalities, defined as values that increase at least one toxicity grade from baseline at any time post baseline up to and including the date of last dose of treatment, will be summarized by treatment group. If baseline data are missing, then any graded abnormality (i.e., at least a Grade 1) will be considered treatment emergent.

Laboratory abnormalities that occur before the first dose of treatment or after the subject has been discontinued from treatment will be included in a data listing.

8.7. Pharmacokinetic Analysis

Pharmacokinetic parameters will be listed and summarized for TAF and TFV using descriptive statistics (eg, sample size, arithmetic mean, geometric mean, % coefficient of variation, standard deviation, median, minimum, and maximum). Plasma concentrations of TAF and TFV over time will be plotted in semi logarithmic and linear formats as mean \pm standard deviation.

For the PK intensive substudy, the following pharmacokinetic parameters will be calculated: C_{max} , T_{max} , C_{last} , T_{last} , C_{tau} , AUC_{tau} , AUC_{last} , CL/F , V/F , λ_z and $t_{1/2}$.

8.7.1. Biomarker Analysis

Selected bone biomarkers, including C-type collagen sequence (CTX) and procollagen type 1 N-terminal propeptide (P1NP), and selected renal biomarkers, including urine retinol binding protein, and urine beta-2-microglobulin, will be summarized by treatment group and visit using descriptive statistics. The difference in change from baseline in these biomarkers between two treatment arms will be tested using Wilcoxon rank sum test.

8.8. Sample Size

With respect to the primary efficacy endpoint, a sample size of 130 for the TDF 300 mg group and 260 for the TAF 25 mg group will have 90% power to rule out the non-inferiority margin of 10% at a one-sided significance level of 0.025. This assumes a rate of 91% in the TDF 300 mg group and 91% in the TAF 25 mg group in the proportion of subjects with HBV DNA < 29 IU/mL. A similar response rate in the TDF group was observed in GS-US-174-0102 {[Marcellin et al 2007](#), [Marcellin et al 2008](#)}.

This sample size (n=260 for the TAF 25 mg arm, n=130 for the TDF 300 mg arm) also provides at least 90% power to detect a 1% difference in the percentage change from baseline in hip BMD at Week 48 (assuming a -1.17% change from baseline in TDF 300 mg arm and -0.17% change from baseline in the TAF 25 mg arm, with a common standard deviation of 2.20% and a two-sided $\alpha = 0.025$); a 77% power to detect a 1% difference in the percentage change from baseline in spine BMD at Week 48 (assuming a -1.69% change from baseline in the TDF 300 mg arm and -0.69% change in the TAF 25 mg arm, with a common standard deviation of 3.08% and a two-sided $\alpha = 0.025$); a 52% power to detect a 0.03 mg/dL difference in the change from baseline in serum creatinine at Week 48 (assuming a 0.04 mg/dL change from baseline in the TDF 300 mg arm and 0.01 mg/dL change from baseline in the TAF 25 mg arm, with a common standard deviation of 0.12). These assumptions were derived from studies GS-98-437, GS-98-438, GS-US-174-0102, GS-US-174-0103, and GS-US-174-0121.

For China, approximately 150 additional subjects (100 subjects TAF 25 mg QD and matched placebo of TDF 300 mg QD, and 50 subjects TDF 300 mg QD and matched placebo of TAF 25 mg QD) will be enrolled.

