This sample size also provides 90% power to detect a 1% difference in the percentage change from baseline in hip BMD at Week 48 (assuming a -1.17% change from baseline in TDF 300 mg arm and -0.17% change in TAF 25 mg arm, with a common standard deviation of 2.20% and a two-sided $\alpha = 0.025$); a 77% power to detect a 1% difference in the percentage change from baseline in spine BMD at Week 48 (assuming a -1.69% change from baseline in the TDF 300 mg arm and -0.69% change in the TAF 25 mg arm, with a common standard deviation of 3.08% and a two-sided $\alpha = 0.025$); a 52% power to detect a 0.03 mg/dL difference in the change from baseline in serum creatinine at Week 48 (assuming a 0.04 mg/dL change from baseline in the TDF 300 mg arm and 0.01 mg/dL change from baseline in the TAF 25 mg arm, with a common standard deviation of 0.12). These assumptions were derived from studies GS-98-437, GS-98-438, GS-US-174-0102, GS-US-174-0103, and GS-US-174-0121.

For China, approximately 150 additional subjects (100 subjects TAF 25 mg QD and matched placebo of TDF 300 mg QD, and 50 subjects TDF 300 mg QD and matched placebo of TAF 25 mg QD) will be enrolled.

This study will be conducted in accordance with the guidelines of Good Clinical Practice (GCP) including archiving of essential documents.

GLOSSARY OF ABBREVIATIONS AND DEFINITION OF TERMS

°C	Degrees Celsius
°F	Degrees Fahrenheit
AASLD	American Association for the Study of Liver Diseases
ADV	Adefovir dipivoxil
AE	Adverse event
AhR	Aryl hydrocarbon receptor
AK	Adenylate kinase
ALT	Alanine aminotransferase (SGPT)
ANC	Absolute neutrophil count
ANCOVA	Analysis of covariance
ANOVA	Analysis of variance
AR	Adverse reaction
AST	Aspartate aminotransferase (SGOT)
AUC _{inf}	Area under the concentration versus time curve extrapolated to infinite time, calculated as $AUC_{0-last} + (C_{last}/\lambda_z)$
AUC _{tau}	Area under the plasma concentration versus time curve over the dosing interval (tau)
bsAP	Bone specific alkaline phosphatase
BMD	Bone mineral density
CatA	Cathepsin A
CD4	Cluster of differentiation 4 cells
CD8	Cluster of differentiation 8 cells
Ces1	Caboxylesterase-1
CHB	Chronic hepatitis B
CI	confidence interval
CKD	Chronic kidney disease
CKF-EPI	Chronic kidney disease epidemiology collaboration
CL/F	Apparent oral clearance after administration of the drug
CL _{Cr}	Creatinine clearance
C _{max}	The maximum observed serum/plasma/peripheral blood mononuclear (PBMC) concentration of drug
COBI / C	Cobicistat

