8.3. Multiplicity Adjustments

The primary hypothesis of non-inferiority between TAF 25 mg QD and TDF 300 mg QD with respect to the proportion of subjects with HBV DNA < 29 IU/mL will be tested first. If non-inferiority is established, then multiplicity adjustments will be performed for the secondary endpoints with a fallback procedure using the following weights:

- a) Hip BMD (weight = 0.4)
- b) Spine BMD (weight = 0.2)
- c) Serum creatinine (weight = 0.4)

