Fasting Urine for Renal Biomarkers ⁱ		X		X		X		X		X	
Fasting Metabolic Panel ^j		X		X		X		X		X	
Urine Pregnancy Test ^k	X	X	X	X	X	X	X	X	X	X	X

Visit windows	Week										
	168	192	216	240	264	288	312	336	360	384/ED ^o	FU ^p
	±28 days										
Urinalysis	X	X	X	X	X	X	X	X	X	X	X
Serum and plasma for storage	X	X	X	X	X	X	X	X	X	X	X (serum only)
Urine for Storage	X	X	X	X	X	X	X	X	X	X	
Ophthalmologic substudy ⁿ – fundoscopic examination with slit lamp										X ⁿ	
Hepatic Ultrasound ^f	X	X	X	X	X	X	X	X	X	X	

- a The visit window for Week 48 visit is –14 days. The visit window for Week 96 is ±14 days.
- b Subjects must rest quietly in the supine position for a minimum of 5 minutes prior to the recording
- c Vital signs include blood pressure, pulse, respiration rate, and temperature
- d DXA scans will be performed only at sites in China with capability. The initial (baseline) DXA will be performed during Screening and should be completed at least 14 days prior to the first dose of study drug. The Week 48 DXA window is –14 days only. DXA is required for Early Discontinuation (ED) visit if not done within the last 24 weeks. Subjects already assigned to open-label TAF 25 mg QD per Amend 2.1 continue on open-label TAF 25 mg QD. Otherwise, blinded study drug will be dispensed until Week 144 visit. Open label TAF will be dispensed from Week 144 through Week 360. At Week 384/ED, study drug will not be dispensed
- f It is preferred that subjects take their study drug according to a morning dosing schedule; subjects who elect to dose in the evening the previous day are not required to have in-clinic dosing and provide the single PK sample being collected at Week 4 and 12 visits.
- g Serum chemistry and Liver Function Tests : alkaline phosphatase, AST, ALT, GGT, total bilirubin, direct and indirect bilirubin, total protein, albumin, LDH, CPK, bicarbonate, BUN, calcium, chloride, creatinine, glucose, phosphorus, magnesium, potassium, sodium, uric acid, and amylase (reflex lipase testing is performed in subjects with total amylase > 1.5 × ULN), and PTH. PTH analyzed at all visits except for Screening through Week 96, and then at Weeks 120, 144, and then every 48 weeks through Week 384/ED. At Baseline, Weeks 24, 48, 72, 96, 120, 144, 192, 240, 288, 336 and 384/ED, subject will be fasting for serum and glucose and metabolic panel. Coagulation panel will be done at Screening and then as a reflex only test for ALT flares.

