1.3. Sample Size and Power

For China, approximately 150 subjects (100 in TAF group and 50 in TDF group) will be enrolled for local registration purposes.

The sample size and power calculation described below was for non-China subjects. With respect to the primary efficacy endpoint of proportion of subjects with plasma HBV DNA levels below 29 IU/mL at Week 48, a sample size of 130 for the TDF group and 260 for the TAF group will have 90% power to rule out the noninferiority margin of 10% at a 1-sided significance level of 0.025. This assumes the expected difference (TAF – TDF) in proportion of subjects with HBV DNA < 29 IU/mL is 0 and the proportion of subjects with HBV DNA < 29 IU/mL in the TDF group is 91%. A similar response rate in the TDF group was observed in Study GS-US-174-0102.

This sample size (n = 260 for the TAF 25 mg group, n = 130 for the TDF 300 mg group) also provides the following:

- At least 90% power to detect a 1% difference in the percentage change from baseline in hip BMD at Week 48 (assuming a –1.17% change from baseline in TDF 300 mg group and –0.17% change from baseline in the TAF 25 mg group, with a common standard deviation (SD) of 2.20% and a 2-sided $\alpha = 0.025$)
- At least 77% power to detect a 1% difference in the percent change from baseline in spine BMD at Week 48 (assuming a –1.69% change from baseline in the TDF 300 mg group and -0.69% change in the TAF 25 mg group, with a common SD of 3.08% and a 2-sided $\alpha = 0.025$)
- At least 52% power to detect a 0.03 mg/dL difference in the change from baseline in serum creatinine at Week 48 (assuming a 0.04 mg/dL change from baseline in the TDF 300 mg group and 0.01 mg/dL change from baseline in the TAF 25 mg group, with a common SD of 0.12)

These assumptions above were derived from Studies GS-98-437, GS-98-438, GS-US-174-0102, GS-US-174-0103, and GS-US-174-0121.

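### The stated BMD power uses a two-sided alpha of 0.025 that the fallback procedure does not use at a total of 0.05, creatinine has no stated alpha, and the DXA footnote read literally conflicts with 260/130

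*Protocol*

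**What the plan says.** **Power.** Protocol 8.8 gives the hip BMD power as "This sample size (n=260 for the TAF 25 mg arm, n=130 for the TDF 300 mg arm) also provides at least 90% power", for a 1-point difference with SD 2.20% at two-sided alpha 0.025. For spine it gives "a 77% power to detect a 1% difference in the percentage change from baseline in spine BMD at Week 48", with SD 3.08% at the same alpha. For creatinine it gives 52% for a difference of 0.03 mg/dL with SD 0.12, and no alpha. The synopsis has the same inputs but a flat figure for hip: "This sample size also provides 90% power to detect a 1% difference in the percentage change from baseline in hip BMD at Week 48". SAP 1.3 repeats the inputs, puts "at least" before all three figures, and says "The sample size and power calculation described below was for non-China subjects".

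**Testing.** Protocol 8.3 tests the three endpoints by a fallback procedure once non-inferiority is shown. The list starts with "a) Hip BMD (weight = 0.4"), followed by spine (0.2) and creatinine (0.4). No total alpha is given.

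**Who is scanned.** Footnote d of Protocol Appendix 2 says "DXA scans will be performed only at sites in China with capability". The synopsis and the visit-by-visit DXA instructions in Protocol 6.2 and 6.3 carry similar wording.

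**The concern.** A power statement should use the significance level at which the endpoint will be tested and the number of subjects who will be measured. Here the level comes from neither the weights nor a stated total alpha, and footnote d puts the number scanned in doubt. Protocol 1.3.3 relies on these figures when it calls the study sufficiently powered for a better bone and renal safety profile. SAP 1.3 turns the spine and creatinine figures into floors, which a reader will take as guarantees at whatever level the procedure reaches.

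**Working it through.** **Inputs.** Sample sizes, differences and SDs are from Protocol 8.8; weights are from Protocol 8.3. Assumptions: total alpha 0.05 two-sided (the level matching the 95% interval in Protocol 8.5.1) and independent tests.

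**Method.** Two-sample t-test. Noncentrality = (difference / SD) / sqrt(1/n1 + 1/n2). At 260/130 the root is 0.1074, so:
- hip: (1/2.20)/0.1074 = 4.23
- spine: (1/3.08)/0.1074 = 3.02
- creatinine: (0.03/0.12)/0.1074 = 2.33

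**Step 1: the plan's own figures.** At two-sided 0.025 these give hip 97.6%, spine 78.0% and creatinine 53.1%. Spine and creatinine match the stated 77% and 52% to within two points. Hip satisfies the wording of 8.8; the flat 90% in the synopsis understates it. Since no alpha is stated for creatinine, 0.025 there is an inference; 0.02 gives 49.7%, also within about two points of 52%.

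**Step 2: fallback levels, total T = 0.05.**
- Hip: 0.4T = 0.02.
- Spine: 0.2T = 0.01 if hip fails; 0.2T + 0.4T = 0.03 if hip is rejected.
- Creatinine: 0.4T = 0.02 if spine fails; 0.02 + 0.01 = 0.03 if only spine is rejected; 0.02 + 0.03 = 0.05 if both are rejected.

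None is 0.025. More generally, hip is tested at 0.4T and spine at 0.6T or 0.2T, so no value of T gives hip and spine the same level.

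**Step 3: power at those levels, 260/130.**

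| Endpoint | Level | Power |
|---|---|---|
| Hip | 0.02 | 97.1% |
| Spine, hip rejected | 0.03 | 80.0% |
| Spine, hip fails | 0.01 | 66.8% |
| Creatinine, both rejected | 0.05 | 64.1% |
| Creatinine, only spine rejected | 0.03 | 56.0% |
| Creatinine, spine fails | 0.02 | 49.7% |

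**Step 4: power through the chain.**
- Spine: 0.9707 × 0.8005 + 0.0293 × 0.6678 = 0.777 + 0.020 = 0.797.
- Creatinine: 0.777 × 0.6412 + 0.020 × 0.5597 + 0.203 × 0.4972 = 0.610.

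So about 97%, 80% and 61%. A simulation with hip-spine correlation 0.5 gives the same rounded figures.

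**Step 5: sensitivity to the unstated total.** With T = 0.025 two-sided, the levels are hip 0.01, spine 0.015 or 0.005, and creatinine 0.025, 0.015 or 0.01. The same calculation gives about 95%, 71% and 49%.

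**Step 6: only if DXA is confined to China.** At most 100/50 are scanned, the root is 0.1732, and the noncentralities are 2.62 (hip) and 1.87 (spine). With T = 0.05, hip power at 0.02 is about 61%. Spine through the chain is 0.608 × 0.378 + 0.392 × 0.235 = 32% under independence, and about 35% with correlation 0.5 (normal approximation). The documents do not give the number of China subjects at DXA-capable sites, so these are upper limits.

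**The case against.** **The stated figures contain no arithmetic error, and the mismatch does little harm.** This largely stands. Step 1 reproduces them, and with a total of 0.05 the chain gives at least what is stated for all three. The 67% for spine applies only when hip fails, about 3% of the time under the design assumptions. What remains is that the level used is not the level of the test. The SAP's floors also fail on the paths where the preceding test fails (spine 67% against 77%, creatinine 50% against 52%), and the comfort depends on a total alpha that nobody has written down.

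**A reader might infer from footnote d that the whole trial scans only in China, so that BMD power collapses.** The documents do not establish this. The Safety part of the synopsis's evaluation criteria schedules BMD assessments with no country limit. It describes fracture risk assessment as a general Baseline item and then restricts it, for China, to sites with DXA capability. SAP 1.3 ties the 260/130 BMD power to subjects outside China, which presupposes scans there. The natural reading is a limit within China. The literal conflict between the footnote and 8.8 is still there and needs a sentence.

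**A reader might also expect a null BMD result in China to be likely and to be misread.** The SAP plans no BMD test: SAP 7.3.1 summarises China BMD descriptively, and Protocol 8.5.2 gives the China analysis the aim of examining consistency. Even if all 150 were scanned and tested, hip power of about 61% would not make a null result the likely one.

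**The non-China Week 48 analysis is already done** (SAP 2). True: restating planning power changes no decision there. It corrects the record and the text that SAP 1.3 carries forward.

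**Conclusion.** The point holds as a mismatch between the power statement and the testing procedure. Assuming a total alpha of 0.05 two-sided and independent tests, power at 260/130 is about 97% for hip, 80% for spine and 61% for creatinine. The stated figures are 90% (synopsis) or at least 90%, 77% and 52%. The error is mostly conservative. That direction is not assured until the total alpha is stated, since a total of 0.025 would give about 95%, 71% and 49%.

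The DXA point is a wording conflict between footnote d and 8.8, not a demonstrated loss of power. The figures of about 61% for hip and 32–35% for spine apply only if DXA is in fact confined to China and all 150 subjects there are scanned. Creatinine needs no scan and is untouched by the DXA restriction.

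**What to change.** 1. In Protocol 8.3, state the total alpha and list the level of each test by path.
2. In Protocol 8.8, the synopsis and SAP 1.3, restate hip, spine and creatinine power at those levels. Give both the power through the chain and the power on each path, and state the alpha for creatinine. With a total of 0.05, the figures are those in Steps 3 and 4. Use the same hip figure in all three places, and drop "at least" where it does not hold on every path.
3. Reconcile footnote d and the matching visit instructions with 8.8 by saying whether sites outside China perform DXA. If they do, the China-only power figures are not needed. If they do not, restate BMD power for the number scanned, at most 100/50.

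The cost is text only: no added subjects, visits or procedures, and no change to the descriptive BMD analysis in the SAP.

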8.9. Data Monitoring Committee

An external multidisciplinary data monitoring committee (DMC) will review the progress of the study and perform interim reviews of safety data and provide recommendation to Gilead whether the nature, frequency, and severity of adverse effects associated with study treatment warrant the early termination of the study in the best interests of the participants, whether the study should continue as planned, or the study should continue with modifications. The DMC may also provide recommendations as needed regarding study design

The DMC will convene approximately every 24 weeks following the time of randomization of the first subject during the blinded portion of the protocol and approximately every 48 weeks during the open-label period.

The DMC's specific activities will be defined by a mutually agreed upon charter, which will define the DMC's membership, conduct and meeting schedule.

While the DMC will be asked to advise Gilead regarding future conduct of the study, including possible early study termination, Gilead retains final decision-making authority on all aspects of the study.

9. RESPONSIBILITIES

9.1. Investigator Responsibilities

9.1.1. Good Clinical Practice

The investigator will ensure that this study is conducted in accordance with the principles of the Declaration of Helsinki (as amended in Edinburgh, Tokyo, Venice, Hong Kong, and South Africa), International Conference on Harmonisation (ICH) guidelines, or with the laws and regulations of the country in which the research is conducted, whichever affords the greater protection to the study subject. These standards are consistent with the European Union Clinical Trials Directive 2001/20/EC and Good Clinical Practice Directive 2005/28/EC.

The investigator will ensure adherence to the basic principles of Good Clinical Practice, as outlined in 21 CFR 312, subpart D, “Responsibilities of Sponsors and Investigators,” 21 CFR, part 50, 1998, and 21 CFR, part 56, 1998.

The investigator and all applicable sub-investigators will comply with 21 CFR, Part 54, 1998, providing documentation of their financial interest or arrangements with Gilead, or proprietary interests in the investigational drug under study. This documentation must be provided prior to the investigator’s (and any sub-investigator’s) participation in the study. The investigator and sub-investigator agree to notify Gilead of any change in reportable interests during the study and for 1 year following completion of the study. Study completion is defined as the date when the last subject completes the protocol-defined activities.

9.1.2. Institutional Review Board (IRB)/Independent Ethics Committee (IEC) Review and Approval

The investigator (or sponsor as appropriate according to local regulations) will submit this protocol, informed consent form, and any accompanying material to be provided to the subject (such as advertisements, subject information sheets, or descriptions of the study used to obtain informed consent) to an IRB/IEC. The investigator will not begin any study subject activities until approval from the IRB/IEC has been documented and provided as a letter to the investigator.

Before implementation, the investigator will submit to and receive documented approval from the IRB/IEC any modifications made to the protocol or any accompanying material to be provided to the subject after initial IRB/IEC approval, with the exception of those necessary to reduce immediate risk to study subjects.

